# LIST OF ABBREVIATIONS AND RELEVANT DEFINITIONS

ABR	General Assessment and Registration form (ABR form), the application form
	that is required for submission to the accredited Ethics Committee; in Dutch:
	Algemeen Beoordelings- en Registratieformulier (ABR-formulier)
ADR	Adverse Drug Reaction
AE	Adverse Event
ΑΙ	Artificial Intelligence
ССМО	Central Committee on Research Involving Human Subjects, in Dutch:
	Centrale Commissie Mensgebonden Onderzoek
CV	Curriculum Vitae
DDGI	Drug-drug-gene interaction
DDI	Drug-Drug Interactions
DNA	Deoxyribonucleic Acid
DPWG	Dutch Pharmacogenomics Working Group
eCRF	Electronic Case Report Form
EU	European Union
FAIR	Findable, Accessible, Interoperable, Reusable
GDPR	General Data Protection Regulation; in Dutch: Algemene Verordening
	Gegevensbescherming (AVG)
НС	Healthcare
ICH-GCP	International Council for Harmonisation of Technical Requirements for
	Pharmaceuticals for Human Use (ICH) Guideline for Good Clinical Practice
	(GCP)
LUMC	Leiden University Medical Centre
MAF	Minor Allele Frequency
METC LDD	Medical Research ethics committee (MREC); in Dutch: Medisch-Ethische
	Toetsingscommissie (METC). LDD: Leiden, Den Haag, Delft
ММС	Medication Management Centre
MP	Data Management Plan
PGx	Pharmacogenomics
ΡοϹ	Proof Of Concept
PRO-CTCAE	Patient-Reported Outcomes version of the Common Terminology Criteria for
	Adverse Events
PROMs	Patient-Reported Outcome Measures
SAE	Serious Adverse Event
SNP	Single Nucleotide Polymorphism

SOP	Standard Operating Procedure
Sponsor	The sponsor is the party that commissions the organisation or performance
	of the research, for example a pharmaceutical company, academic hospital,
	scientific organisation, or investigator. A party that provides funding for a
	study but does not commission it is not regarded as the sponsor but referred
	to as a subsidising party.
UAVG	Dutch Act on Implementation of the General Data Protection Regulation; in
	Dutch: Uitvoeringswet AVG
UKA	University Hospital Aachen
UL	University of Ljubljana
UPAT	University of Patras
U-PGx	Ubiquitous Pharmacogenomics
UUID	Universal Unique Identifier
WMO	Medical Research Involving Human Subjects Act; in Dutch: Wet Medisch-
	wetenschappelijk Onderzoek met Mensen

#### SUMMARY

**Rationale**: In current clinical practice, polypharmacy and patient empowerment are critical yet often overlooked. Polypharmacy, the chronic use of five or more drugs, poses risks such as adverse drug reactions and decreased medication adherence, especially in elderly and multi-morbid patients. Despite the interconnected nature of drug-drug and drug-gene pro interactions, they are considered separately. Ignoring these interactions can be hazardous, yet clinical trials to investigate them are infeasible due to fast-growing complexity, variability among patients, high costs associated with large-scale studies, and ethical and logistical challenges. Consequently, there is a substantial knowledge gap in managing complex medication regimens in real-life scenarios and providing guidelines to enhance patient empowerment and drug safety. The SafePolyMed project aims to develop a patient-centred framework to define, assess and manage drug-drug, drug-gene and drug-drug-gene interactions. This framework, a web-based medication management centre, will support patients in managing their therapy-related health data, enhancing education and empowerment, and improving patient safety.

**Objective**: To assess the impact of the developed medication management centre on patient empowerment in polypharmacy patients, thereby improving drug safety. Secondary objectives are to explore if the tool is able to identify patients at risk for a drug-drug-gene interaction and lower the adverse drug event rate.

**Study design**: The study is a proof of concept study conducted at four institutes located in Germany, Greece, Slovenia and The Netherlands. Polypharmacy patients will use the medication management centre (MMC), which provides curated, patient-specific information about drug interactions and PGx. To assess patient empowerment, patients will receive question-naires during a 12 week follow-up period.

**Study population**: 120 subjects with polypharmacy (defined as the chronic use of 5 or more drugs) of at least 18 years of age, with a first prescription for one of 10 index drugs. The study will be performed at 4 different sites (Leiden (NL), Patras (GR), Ljubljana (SL), Aachen (DE)) to represent different clinical settings across Europe. Each site will recruit 30 patients.

**Intervention**: The MMC that provides patient centred information on drug-drug interactions and pharmacogenetics affecting personal polytherapy. The MMC will show a selection of high quality publicly available information such as details on different types of medications, including their uses, side effects and instructions for use, in the language of the patient. This information is targeted at an individual patient's medication profile to inform patients to better understand and deal with their personal health information, with regard to drug therapy. Patients in the Netherlands, Slovenia and Greece also will receive their PGx profile to further personalise the MMC experience.

**Main study parameters/endpoints**: The primary outcome is the sense of empowerment and health literacy for participants before and after use of the MMC. Secondary outcomes include an evaluation of the drug-drug-gene interactions and adverse drug events in the study populations compared to matched historical controls.

Nature and extent of the burden and risks associated with participation, benefit, and group relatedness: Patients are exposed to the regular treatment. In addition, patients will receive questionnaires at baseline, two, and twelve weeks regarding the use and experience of the medication management centre, and a close-out interview at week twelve. In addition, 10ml of blood will be collected during a venipuncture for pharmacogenetic analyses.

Benefits include having access to the medication management centre for the duration of the study. Additionally, patients will receive their PGx profile. This can be used to individualize drug treatment, based on the Dutch Pharmacogenetics Working Group (DPWG) guidelines.

Overall, minimal risks are expected for subjects as they will receive normal clinical care. Information from the MMC will be a curation of existing publicly available data. Any information regarding DDIs and DGIs will be supplemented with a disclaimer that the patient should not adjust their treatment without talking to a healthcare provider.

#### **1. INTRODUCTION AND RATIONALE**

Adverse drug reactions (ADRs) are a major burden to our healthcare (HC) and economic systems. In the European Union (EU) alone, approximately 197,000 deaths annually are attributed to ADRs.(1) Polypharmacy, multimorbidity and genetic heterogeneity can affect drug efficacy, raise the risk for ADRs and consequently increase healthcare costs. This issue is exacerbated by the growing prevalence of polypharmacy (the chronic use of five or more medications concomitantly) which affects 26 to 40% of elderly European citizens.(2)

Public education on drug intake, polypharmacy, and individual medication risks remains insufficient. This contributes to weakened patient security, poor medical adherence, and suboptimal therapy outcomes.(3; 4) Elderly individuals, polymedicated patients, and those with multiple chronic conditions often face challenges in managing their health, potentially leading to increased healthcare needs. Systematic documentation of health status using patient-reported outcome measures (PROMs) is crucial for early identification of ADR-related issues and enhancing communication between patients and healthcare providers. A comprehensive approach involving patient education and active participation in documenting therapy-related health status can empower patients, improve treatment outcomes, and reduce ADRs.(5; 6)

The SafePolyMed project aims to develop a patient-oriented framework for defining, assessing, and managing drug-gene product interactions (DGIs) and drug-drug interactions (DDIs). This framework will support patients in managing their therapy-related health data, improving education, patient empowerment, and patient safety. Tools for PROM management, DDI information, and DGI information will be integrated into a web-based Medication Management Centre (MMC). This tool will help patients manage and monitor their therapies, educate them about their therapy, thereby empowering the patients by creating a sense of participation in the decision process when it comes to the management of their diseases. The information in this tool is curated publicly available information. Moreover, novel tools that uses machine learning and mechanistic modelling techniques using relevant real-world datasets to assess patients at risk for ADRs have been developed but are not yet clinically validated. These tools can be integrated into the MMC to show interconnectability but are not yet validated and therefore not reported to patients or used for drug management, this is a separate part of the overarching SafePolyMed consortium. Additionally, the MMC will be used to collect patient-reported outcomes.

To assess the impact of the developed medication management centre on patient empowerment in polypharmacy patients to improve drug safety, we will execute a transnational proofof-concept study.

# 2. OBJECTIVES

# 2.1 Primary objective

The primary objective is to assess the impact of the developed medication management centre on the patient empowerment of polypharmacy patients, thereby improving drug safety.

# 2.2 Secondary objective

To investigate if the medication management centre is able to identify patients at risk for a drug-drug-gene interaction. Moreover, it will be investigated whether integrating the MMC into healthcare will lower the adverse drug event rate compared with matched historical control.

# 3. STUDY DESIGN

## 3.1 Overall study design

This study is a multi-centre, open-label study to assess the impact of the developed MMC in combination with the developed risk score algorithms, patient-reported outcome tool, and model-based precision dosing tool on patient empowerment of polypharmacy patients, thereby improving drug safety. In the study, a total of 120 patients will be enrolled in The Netherlands, Greece, Slovenia, and Germany (30 patients per country). The study subjects will be followed for 12 weeks. At set time intervals (2 and 12 weeks) the subjects will be asked to complete a validated questionnaire through the eClinical Data Management Platform Castor (table 1), for which the patients receive an email and a reminder through the MMC. These questionnaires collect information on the experience with the MMC, clinical monitoring, clinical outcome, and adverse events.

Table 1. Overview of the questionnaires during the 12-week follow-up. The baseline questionnaire comprises of 97 questions, the 2-week questionnaire of 133 questions and the 12-week questionnaire of 206 questions. All questionnaires are adaptive.

	Baseline questionnaire	Adaptive questionnaire in the MMC at time point:	
		2 weeks	12 weeks
Experience			
Usability		Х	х
Health literacy	х		х
Clinical monitoring			
Comorbidities and allergies	х		
Concurrent medication and herbal	х	х	х
remedies (through patient diary)			
Clinical outcome			
Drug adherence	х	Х	х
Quality of Life	х		х
Adverse events			
Patient reported ADR		Х	х
Assessment of ADR severity		х	х
Pharmacogenomics			
DNA sample collection	Х		

The baseline questionnaire will additionally comprise questions covering in- and exclusion criteria, demographics, recruitment information, previous PGx test results, comorbidities and allergies, and the level of health literacy before use of the MMC. In total, the baseline questionnaire consists of 97 questions. The questionnaire offered two weeks after inclusion in the study consists of 133 questions. The last questionnaire, offered 12 weeks after inclusion in the study, consist of 206 questions. All questionnaires are adaptive meaning that the length and duration of the questionnaire depends on the answers of the participants.

[figure not shown]
Effectiveness in the prevention of ADRs and the ability to identify drug-drug-gene interactions will be explored as a secondary endpoint by comparing results of the pilot study with those obtained from matched historical controls obtained from the control arm of the U-PGx project. This control arm is suitable as historical control group for the EmPaSafe study because of its alignment in key aspects, allowing for meaningful comparisons:

- Genotyped but not empowered with PGx Data: Participants in the U-PGx control arm were genotyped retrospectively, meaning their PGx information was available but not actively utilized in their care. This setup provides a unique baseline to assess the effectiveness of the MMC and the empowerment of EmPaSafe patients with PGx data, as we can analyse whether access to their genetic information and medication adjustments reduces ADRs and improves drug efficacy.
- Comparable Follow-up and Monitoring Protocols: The U-PGx control arm and the EmPaSafe study share similar follow-up methods, including regular monitoring for ADRs and the use of similar questionnaires. This similarity minimizes variation in data collection processes, allowing us to more directly compare ADR prevalence and other outcomes between the two groups.
- Matching for Key Variables: The control group will be matched to EmPaSafe participants based on age, sex, and type and number of medications, controlling for these variables in the analysis. This matching enhances the comparability of the two cohorts and strengthens the reliability of conclusions drawn about the impact of empowering patients with PGx data through the MMC.

Using the U-PGx control arm as a historical comparison thus allows EmPaSafe to evaluate the added value of PGx-informed care without needing a concurrent control group, streamlining the study while leveraging pre-existing data to explore the MMC's role in improving medication safety and personalization.

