#### 3.2 Patient journey

The patient journey starts when the patient receives a first prescription for one of the index drugs (see table 3). Upon enrolment, patients get access to the MMC. The day of the first prescription is considered T=0.

Medication Management Centre

The MMC will offer patients curated, personalised information regarding DDIs and DDGIs and a patient diary to manage and monitor their drug therapy. Additionally, the MMC will remind the patients by email to complete a questionnaire through the eClinical Data Management Platform Castor These questionnaires collect information on the experience with the MMC, clinical monitoring, clinical outcome, and adverse events, according to the schedule in table 2. Patients can report ADRs in the medication management centre through patient reported outcome measures (PROMs) in the patient diary. More information regarding the MMC can be found in section 5.1.1.

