# 3.3 Data collection procedures

T=0 is defined as the day the patient initiates the index drug (table 3). During the 12-week follow-up period, the patients will receive surveys at baseline, 2 weeks and 12 weeks and a semi-structured close-out interview at week 12. Patients are requested to complete the surveys within a week. In case a patient discontinues the index drug within the 12-week follow-up period, the follow-up will continue as initially anticipated. The questionnaires will be provided to the patients through the medication management centre.

The data collected by the surveys is summarized in table 2. The MMC will collect: 1) Data entered by patients: demographic information, medical information, symptom diary, 2) Data created by the MMC and its tools: medication plan assessed with its safety risks (DDIs, DGIs, risk score, dosing information) and 3) statistical information collected by the system about the usage of the system by individual patients, sub-cohorts and the whole cohort.

All data will be entered into an electronic Case Report Form (eCRF), which guarantees consistency of data collection procedures. Data will be used exclusively in a pseudonymous fashion and data protection will be guaranteed according to international regulations. Local, independent internal monitors will guarantee data integrity and data homogeneity across all four implementation countries by risk-based monitoring of a random sample of the collected data. The research team will collect and store patient contact information (e-mail address, telephone number, name, and study-ID number) in a separate, local file (national subject identification code list).

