#### 5.1.1 The medication management centre

All patients participating in the EmPaSafe study will gain access to the Medication Management Center (MMC), a digital platform developed to empower patients with information and enhance medication safety, particularly in cases of polymedication. The MMC's primary purpose is to serve as an educational resource that provides tailored, patient-specific insights into drug-drug interactions (DDIs) and drug-drug-gene interactions (DDGIs) based on individual pharmacogenomic (PGx) profiles. These insights aim to support adherence to therapy, improve patient outcomes, and mitigate risks associated with complex medication regimens.

The MMC annotates each patient's medication plan with curated safety information sourced from validated guidelines, including those from the Dutch Pharmacogenetics Working Group (DPWG), and trusted public databases such as the ABDA-Database. By offering personalized, high-quality content, the MMC helps patients understand their therapies and the potential risks associated with their medications. It also provides tools for reporting health concerns, such as adverse drug reactions (ADRs), through integrated patient-reported outcome measures (PROMs).

A core feature of the MMC is its emphasis on patient engagement. The platform equips users with the knowledge to have meaningful discussions with healthcare providers, thereby fostering collaborative decision-making. However, the MMC strictly serves an informational purpose; it neither facilitates self-adjustment of medication nor replaces professional medical advice. This distinction ensures compliance with regulatory requirements and underscores its role as an educational rather than a diagnostic tool.

The MMC also includes advanced functionalities that may shape the future of personalized medicine. These include exploratory tools, such as machine learning models and mechanistic risk assessments, designed to analyse real-world data for predicting adverse drug reactions (ADRs). While these tools are not yet clinically validated, they represent the innovative potential of integrating cutting-edge technologies into medication management.

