### Secondary clinical outcome:

- Total number of ADEs (related to index and subsequent drugs)
- Dose adjustments to index drug
- Drug cessation (and reason for discontinuation)
- Additional drugs that are prescribed during follow-up
- Routine drug levels (only those that are collected routinely) as a proxy for exposure
- Patient-reported drug adherence

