# 9.2 AEs and SAEs

# 9.2.1 Adverse events (AEs)

AEs reported by the patient will be followed up until they have abated, or until a stable situation has been reached, as done within the realm of routine clinical care. AEs will be monitored via patient reporting through the medication management centre.

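### The U-PGx comparison of adverse drug events is justified by similar data collection, yet only EmPaSafe patients have the MMC diary, and the ADE outcome does not say whether diary reports count

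*Protocol*

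**What the plan says.** The secondary objective (protocol section 2.2) asks whether "integrating the MMC into healthcare will lower the adverse drug event rate compared with matched historical control". The controls come from the control arm of U-PGx, matched on age, sex, and type and number of medications (sections 3.1 and 4.4).

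Section 3.1 gives comparable monitoring as one of three reasons why this arm is suitable: "The U-PGx control arm and the EmPaSafe study share similar follow-up methods, including regular monitoring for ADRs and the use of similar questionnaires". From this it concludes: "This similarity minimizes variation in data collection processes, allowing us to more directly compare ADR prevalence and other outcomes between the two groups".

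On how EmPaSafe collects adverse reactions, the protocol says:

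- Table 1 in section 3.1 places patient-reported ADRs and their severity at weeks 2 and 12. Section 5.1.2 names PRO-CTCAE among the instruments at those time points.
- Section 3.2 adds: "Patients can report ADRs in the medication management centre through patient reported outcome measures (PROMs) in the patient diary".
- Section 3.3 lists among the data that the MMC collects: "1) Data entered by patients: demographic information, medical information, symptom diary".
- Section 5.1.1 describes ADR reporting as a function of the MMC.
- Section 9.2.1 states: "AEs will be monitored via patient reporting through the medication management centre".

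The Summary, under Intervention, says that the MMC shows patients information on their medicines, including side effects, targeted at their own medication profile. The outcome list in section 8.1.2 opens with "Total number of ADEs (related to index and subsequent drugs" and names no reporting source.

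**The concern.** The tool under study is also a tool for reporting ADRs. A patient in EmPaSafe has the scheduled questionnaires plus a diary. A U-PGx control, as described here, had regular monitoring and similar questionnaires, and cannot have had this diary, because the MMC is a product of the present project (section 1). If diary reports enter the EmPaSafe count, part of any difference in ADE rates reflects how events were found and not how many occurred. The matching variables do not touch this, so better matching would not help.

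The likely direction is against the MMC. Section 1 itself argues that systematic patient-reported documentation helps to identify ADR problems early, which implies better detection where the tool is used. A true reduction could then be diluted, hidden or, in a bad case, shown as an increase. Section 4.4 says that the results will help to design a larger study, so a distorted estimate would be carried into that planning.

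**Working it through.** **No figure to reproduce.** The protocol states no ADE rate, effect size or capture rate, and section 4.4 says that no formal power calculation was done. The check therefore has two parts: which sources the text allows into the count, and how the result responds to assumed capture rates.

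**1. Which source feeds the ADE count?**

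- *Pointing to questionnaires only:* Table 1 (ADR rows at weeks 2 and 12), section 5.1.2 (ADRs obtained by the standardized questionnaires), and section 8.3 (adverse-event questionnaires at 2 and 12 weeks; questionnaire and genetic data named for the descriptive analysis of the main endpoints).
- *Leaving the diary open:* sections 3.2 and 5.1.1 (ADRs can be reported in the MMC), section 3.3 (the symptom diary is collected data), and section 8.1.2 (a total count with no source).
- *Ambiguous:* section 9.2.1. Section 3.3 says that the questionnaires are themselves provided through the MMC, so reporting through the MMC may mean only those.

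No passage includes diary events in the count and none excludes them.

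**2. What follows if diary events are counted?**

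Let RR be the true ADE rate ratio (EmPaSafe to controls), *c* the share of ADEs that questionnaires capture in either cohort, and *e* the share captured by questionnaires plus diary. Count an event reported by both routes once. Then:

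observed ratio = RR × (*e* / *c*)

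The apparent benefit vanishes when *e* / *c* = 1 / RR. For RR = 0.80 that is 1 / 0.80 = 1.25.

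All capture rates and the true ratio of 0.80 are assumptions:

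| *c* | *e* | *e* / *c* (also the observed ratio if RR = 1) | Observed if RR = 0.80 |
|---|---|---|---|
| 90% | 95% (diary finds half of the missed 10%) | 0.95 / 0.90 = 1.06 | 0.84 |
| 70% | 85% (diary finds half of the missed 30%) | 0.85 / 0.70 = 1.21 | 0.97 |
| 60% | 80% (diary finds half of the missed 40%) | 0.80 / 0.60 = 1.33 | 1.07 |
| 70% | 95% (diary finds 25 of the missed 30 points) | 0.95 / 0.70 = 1.36 | 1.09 |

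With near-complete questionnaire capture the distortion is small. With moderate capture and an active diary it can remove or reverse a 20% reduction.

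**3. What follows if diary events are not counted?**

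Then *e* / *c* = 1 and a true 0.80 is seen as 0.80, apart from one residue: patients who have been shown the side effects of their own drugs may report more even on the shared questionnaires. The formula does not size that effect.

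**The case against.** The strongest reply is that the plan may already do the right thing. Every passage that ties ADR data to a time point names the week 2 and week 12 questionnaires, and the choice of source for an ADE count is ordinary content for a statistical analysis plan, which is not at hand. This stands in part. A reader might infer that diary events are counted and that the comparison is therefore biased; the documents do not support that, because they never say that diary entries enter the total.

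Three further limits also stand:

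- A reader might infer that controls had no unscheduled way to report ADRs. Section 3.1 gives only a one-sentence description of U-PGx follow-up, so another route cannot be ruled out. It was not the MMC diary.
- Section 3.1 claims similarity, not identity, and no diary frequency is stated, so it should not be assumed that reporting was continuous.
- A reader might infer that reversal of a benefit is to be expected. It appears only under some assumed capture rates.

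The exploratory status of the comparison (sections 3.1 and 4.4) and its descriptive analysis (section 10.2) lower the stakes. They do not answer the point, since a descriptive estimate is distorted by unequal detection just as a tested one is.

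What the reply does not reach is the statement in section 3.1 itself. It asserts comparable data collection now, without a restriction to questionnaire events and without mention of the diary or the side-effect information.

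**Conclusion.** The point holds in a conditional form. The comparability claim in section 3.1 leaves out a reporting route and an information effect that belong to the intervention, and section 8.1.2 does not close the gap by naming a source. If diary reports are counted, detection is likely to be higher in EmPaSafe and the comparison is tilted against the MMC. If they are not counted, only awareness-driven reporting remains.

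The documents do not fix the size. The range of about 0.84 to 1.09 for a true ratio of 0.80 rests wholly on assumed questionnaire capture of 60% to 90%, on assumed diary yield, and on equal questionnaire capture in both cohorts.

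This is a cheap improvement of low severity: the outcome is secondary, the analysis is descriptive, and no decision rule depends on it.

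**What to change.** 1. In sections 3.1 and 8.1.2, state that the U-PGx comparison uses only ADEs reported on the scheduled questionnaires, with items and recall windows present in both studies.
2. Record the source (questionnaire, diary or both) of each EmPaSafe ADE. Set this up before data collection, since the source may be hard to reconstruct later. Report diary-only events separately, without a control comparison.
3. Qualify the comparability sentence in section 3.1, for example: *Scheduled ADR questionnaires are similar in the two studies. MMC users have an additional reporting route, and they see side-effect information that may raise reporting even on the shared questionnaires; the comparison is therefore limited to questionnaire-reported events and is interpreted with this in mind.*

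The cost is a few lines of wording and one field per ADE record. Diary-only events leave the control comparison but stay in safety reporting. Awareness-driven reporting cannot be removed in this way and remains a stated limitation.

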# 4.4 Sample size calculation

As this is a proof-of-concept (PoC) pilot study, the sample size is aimed at showing the impact of the use of the MMC on patient empowerment and exploring associations, rather than statistically significant relations. Therefore, no formal sample size and power calculation is done. A number of 30 participants per site is the number of subjects that we estimate to be sufficient to investigate the impact of using the medication management centre and associated tools.

To explore potential effectiveness of the tool, results will be compared with those of matched historical controls obtained from the control arm of the U-PGx project. While the study is not aimed at or powered for statistical comparisons, we are in the unique position to have a access to a substantial cohort of comparable patients. Controls will be matched for age, sex and type and number of mediations. These results will help to design a larger study to perform a formal statistical analysis of the effect of the medication management system and associated tools.

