# 8.1.2 Secondary study parameters/endpoints (if applicable)

Secondary analyses are aimed at defining the ability of the MMC to accurately identify patients at risk for a drug-drug-gene interaction. The effect of integrating the MMC into healthcare on the incidence of adverse drug events compared to matched historical controls from the U-PGx cohort will also be assessed.

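### The exploratory U-PGx comparison names no country or site in its matching, does not say how the 30 ungenotyped German patients enter it, and cannot isolate a PGx effect as section 3.1 claims

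*Protocol*

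**What the plan says.** **Matching.** Section 3.1 states: "The control group will be matched to EmPaSafe participants based on age, sex, and type and number of medications". Section 4.4 gives the same variables: "Controls will be matched for age, sex and type and number of mediations". Country and site appear in neither.

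**Sites.** Table 2 in section 4.1 gives each centre its own focus: community pharmacies in Leiden, a psychiatric clinic in Patras, primary care in Ljubljana, and an outpatient clinical pharmacology unit in Aachen for patients above 60. Centres may recruit outside their focus. Section 3.1 itself describes Germany as different in law, health care and culture.

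**What patients receive.** All 120 patients get the MMC (sections 5.1.1 and 8.3). The Dutch, Greek and Slovenian patients also get PGx testing and the German patients do not (sections 3.1 and 8.2). PGx results go to the patient through the MMC, and physicians learn only what the patient passes on (section 3.2). The controls were genotyped retrospectively, "meaning their PGx information was available but not actively utilized in their care".

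**Interpretation.** Section 3.1 says that using this control arm "allows EmPaSafe to evaluate the added value of PGx-informed care without needing a concurrent control group", and that "we can analyse whether access to their genetic information and medication adjustments reduces ADRs". Two other sections attribute the adverse drug event (ADE) comparison to the MMC. Section 2.2 asks "whether integrating the MMC into healthcare will lower the adverse drug event rate compared with matched historical control". Section 8.1.2 names "The effect of integrating the MMC into healthcare on the incidence of adverse drug events compared to matched historical controls from the U-PGx cohort".

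**Status.** The comparison is exploratory and not powered (sections 3.1 and 4.4), and secondary outcomes are analysed descriptively (section 10.2).

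**The concern.** Three features of one comparison need attention.

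1. ADE recording and background risk can differ between health systems and recruitment settings. Without site in the matching or the analysis, such a difference can appear as an effect of the intervention.
2. Sections 3.1 and 4.4 and the Summary describe the comparison for the pilot as a whole. A quarter of the patients receive a different intervention from the rest, and nothing says whether they are included, excluded or shown apart.
3. Section 3.1 offers the comparison as a way to judge PGx-informed care without a concurrent control. The design does not support that, because nobody receives PGx without the MMC.

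What is at stake is how a secondary result is read, and what is carried forward from it. Section 4.4 says: "These results will help to design a larger study to perform a formal statistical analysis". The primary endpoint, a before-and-after assessment of empowerment and health literacy, does not use these controls and is unaffected.

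**Working it through.** **Inputs.** 30 patients in each of four countries (sections 3.1 and 4.1); PGx in the Netherlands, Greece and Slovenia only (section 8.2); MMC for everyone (section 8.3). That the controls had no MMC is an inference from section 3.1, which treats them as the baseline for judging it. The protocol gives no ADE rates, number of controls, alpha or power.

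**Step 1: reproduce the total and split it.**
- 4 × 30 = 120, as stated.
- MMC plus PGx: 3 × 30 = 90, and 90/120 = 75%.
- MMC only: 30, and 30/120 = 25%.
- PGx without MMC: 0.

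**Step 2: what each contrast estimates.** Let m be the effect of the MMC and g the effect of PGx feedback, assumed additive, against controls with neither.
- The 90 genotyped patients: m + g.
- The 30 German patients: m.
- All 120 pooled: (90(m + g) + 30m)/120 = m + 0.75g.

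None of these is g. Suppose, purely for illustration, that m + g is 10 percentage points:

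| m | g | 90 genotyped | 30 German | All 120 |
|---|---|---|---|---|
| 0 | 10 | 10 | 0 | 7.5 |
| 5 | 5 | 10 | 5 | 8.75 |
| 10 | 0 | 10 | 10 | 10 |

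The result in the 90 is the same whether PGx accounts for all of the effect or none of it.

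**Step 3: can the German result be subtracted?** Let the MMC effect be m1 at the genotyping sites and m0 in Germany, and let b1 and b0 be the errors left by imperfect historical matching. The difference between the two contrasts is

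(m1 + g + b1) − (m0 + b0) = g + (m1 − m0) + (b1 − b0).

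PGx status coincides with country, and the German site focuses on patients above 60 in one type of clinic. Nothing in the design makes the last two terms zero.

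**Step 4: site omitted from the matching.** Let r_s be the ADE rate that would be recorded at site s without the intervention, and w_st the share of site s's matched controls that come from site t. With no intervention effect, the expected difference at site s is Σ_t w_st (r_s − r_t). It vanishes if all controls come from the same site or if the rates are equal. Matching on age and medication type makes the rates more alike, but does not deal with differences in health system or reporting. The documents give neither w nor r, so no number follows.

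**Step 5: drug-drug-gene interactions.** The same sentence of section 3.1 covers detection of these interactions. German patients are not genotyped in the study, and section 4.3 excludes anyone previously genotyped for PGx genes. That part can be evaluated only in the 90.

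**Step 6: precision cost of using 90 instead of 120.** The half-width of a 95% interval for a proportion in the EmPaSafe group is 1.96 × √(p(1 − p)/n).
- p = 0.5 (assumed): 8.9 points at n = 120, 10.3 at n = 90.
- p = 0.2 (assumed): 7.2 points at n = 120, 8.3 at n = 90.
- Ratio: √(120/90) = 1.155, about 15% wider.

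**The case against.** The case against has real force, and much of it stands.

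- **Site handling can be left to an analysis plan.** The matching lists do not say that no other variable will be used, and a plan that is not shown could stratify or adjust by site. That is fair. But the protocol gives the same list in two places and presents it as what makes the cohorts comparable, so the gap is worth closing there.
- **No pooled PGx estimate is prescribed.** A reader might infer that all 120 will be pooled to estimate a PGx effect. The documents do not say so. Section 3.1 justifies the German site by empowerment, health literacy and generalisability beyond PGx. What stands is that the comparison is worded for the whole pilot and the German patients' place in it is not stated.
- **Section 3.1 elsewhere names the package.** Its other wording speaks of PGx data delivered through the MMC, and the criticised sentence ends on the MMC's role. True, but the two claims quoted from that section still credit PGx.
- **Sections 2.2 and 8.1.2 might look wrong too.** They are not. They name the MMC, which every participant receives. Rewording them as MMC plus PGx would be false for the German patients.
- **The larger study might seem compromised.** The sentence in section 4.4 goes on to name the medication management system and its tools as the target, not PGx alone. Failure to isolate PGx therefore does not clearly damage it.
- **Appendix 4 might seem to give the size of the site problem, or to show that no German controls exist.** It supports neither. Its counts served to choose index drugs, are not stated to be control-arm counts, and come from PREPARE, which the protocol does not expressly equate with the U-PGx cohort. It shows only the Leiden, Ljubljana and Patras centres, so the availability of German controls is open.

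**Conclusion.** The point holds as a minor-to-moderate one. Country or site is missing from both matching lists, the handling of 30 of 120 patients (25%) is not stated, and the claim in section 3.1 about PGx-informed care is wrong as written. The comparison can show MMC plus patient-held PGx feedback versus neither in 90 patients, and MMC alone versus neither in 30. An all-patient result would be a 75:25 mix of the two. No PGx effect can be isolated from these contrasts.

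This rests on the controls having had no MMC, which is implied rather than stated. The m + 0.75g expression also assumes additive effects, but the failure to isolate PGx does not depend on additivity. No size of bias is claimed for the omission of site. The comparison is secondary, descriptive and unpowered.

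**What to change.** 1. In sections 3.1 and 4.4, add country or site to the matching where the control pool allows; otherwise stratify or adjust by site. State whether German controls are available.
2. Make the PGx-related and drug-drug-gene comparisons in the 90 genotyped patients. Report the 30 German patients separately as MMC only. Label any all-patient ADE result as a 75:25 mix of the two interventions.
3. In section 3.1 only, replace the claim about PGx-informed care with an exploratory comparison of the MMC plus PGx feedback (the Netherlands, Greece, Slovenia) versus historical care with neither. Qualify the clause on access to genetic information in the same way. Leave sections 2.2 and 8.1.2 worded as the MMC, at most noting that it includes PGx feedback at three of the four sites.

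These are changes of analysis and wording and need no new data. The cost is 90 rather than 120 patients in the PGx-related comparison, with intervals for the EmPaSafe group about 15% wider, and smaller control strata once site is used.
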